### **3 INTERIM ANALYSES**

There are no formal interim analyses planned for this study. Safety data required as part of the EMA Risk Management Plan (RMP) for tafamidis will be analysed and submitted annually. One or more data extracts will be performed annually in order to support ad hoc analyses for publications and for pricing and reimbursement.

A Scientific Board comprised of selected participating physicians, clinical experts and representatives from the Sponsor will oversee data review and analysis of pooled THAOS data collected from all participating sites. The Board will advise on scientific and policy decisions regarding amendments to the survey protocol and publication of THAOS data. Participating physicians may recommend to the Board the addition of specific analyses of data, or new questions to explore based on available results. The roles and responsibilities of the Board are detailed in a separate charter.

### **4 HYPOTHESES AND DECISION RULES**

There are no hypotheses associated with this survey. All analyses will be descriptive.

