Data will be recorded from all patient visits and entered into the THAOS electronic data record as soon as possible after the visit is complete. Data will be entered into a secure, confidential computer-based application which allows for remote data entry through locally secured connections. A Scientific Board representing the THAOS physicians will meet at least annually and recommend statistical analyses.

Each survey site will be required to obtain local Institutional Review Board (IRB)/Ethics Committee (EC) approval to participate in THAOS and before enrolling patients.

There is no pre-determined number of enrolled patients or participating sites in THAOS. The survey will be conducted at sites worldwide.

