### **9.7.2. Data Summaries**

THAOS data will be available for analysis on 3 different levels: by patient, by individual survey site, and across survey sites.

The primary objective of the survey is to better understand the natural history of ATTR (hereditary and wild-type forms) and the progression of disease in this patient population. Analysis of clinical outcomes will be conducted on all enrolled patients with available data. Outcomes will be examined for the entire patient group, as well as through stratification of important variables that may affect outcomes (for example, but not limited to, TTR variant, age, race, gender, country of origin). Outcomes will include results of the key clinical, functional and QoL assessments used to define progression of disease.

Data will be summarized descriptively and modeled using appropriate statistical methodology.

THAOS physicians may use the THAOS electronic clinical database to obtain ongoing longitudinal data on their individual patients to assist them in following and caring for their patients. A physician can extract their individual survey site data for an individual or all patients enrolled at the survey site to identify trends in the data and/or assist in patient care and monitoring at their survey site.

THAOS physicians may request or share data across survey sites. A request may pertain to available information on patients with a newly identified TTR variant, or on a subset of patients to assist a THAOS physician with the clinical management of a patient (or patients), or to provide information pertinent to research interests across survey sites. Requests for data should be forwarded to the Sponsor for processing and will be promptly reviewed.

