### **9.9. Limitations of the Research Methods**

The observational nature of this study has the potential to introduce selection or ascertainment bias. The study population could be more heterogeneous. Confounding leads to biased estimates of associations of risk factors or treatment with outcome and thus impacts the validity of the conclusions from the study. Analytical methods (like matching, multivariate regression) would be used to control for confounding.

Other potential limitations to the validity of the study include missing data and loss to follow-up or censoring. Appropriate statistical methods would be employed to account for missing data and described in the SAP. Sensitivity analysis to assess the impact of loss to follow-up will also be explored.

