## 2 INTRODUCTION

The Transthyretin-Associated Amyloidosis Outcomes Survey (THAOS) is a non-interventional, global, multi-center, longitudinal, observational survey open to all patients with Transthyretin (ATTR) amyloidosis, including both due to TTR variants (ATTRv) and wild-type forms of the disease (ATTRwt), and patients with TTR gene variants (previously referred as mutations) without disease diagnosis. At the inception of THAOS, limited data were available on the natural history of the ATTRv and ATTRwt forms of the disease, including the regional differences in disease expression by TTR variants and non-mutated TTR, and the genotypic-phenotypic relationship in ATTR.

The objectives of THAOS are to describe the population of patients affected with ATTR amyloidosis and to enhance the understanding of the disease natural history, including the variability and progression of the hereditary and acquired forms of disease by studying a large and heterogeneous patient population. Survey data may be used to develop new treatment guidelines and recommendations, and to inform and educate clinicians about the management of this disease.

The survey can also generate descriptive safety summaries using adverse events (AE) and serious adverse events (SAE) data in tafamidis-treated patients. AE/SAE data collection in THAOS will be utilized in the post-marketing setting to provide additional information on the safety of tafamidis over the longer term as well as its effect on survival. Additionally, the collection of safety data in THAOS will fulfill part of the post-marketing commitment to the Committee for Medicinal Products for Human Use

PFIZER CONFIDENTIAL

(CHMP) for tafamidis. Specifically, this non-interventional (NI) study is designated as a Post-Authorization Safety Study (PASS) and is a commitment to the European Medicine Agency (EMA).

The objectives of THAOS are to describe the population of patients affected with ATTR amyloidosis and to enhance the understanding of the natural history of ATTR amyloidosis, including the variability and progression of the hereditary and acquired forms of disease.

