## 2.2 STUDY OBJECTIVES

The objectives of THAOS are to:

- Describe the population of patients affected with ATTR amyloidoses;
- Enhance the understanding of disease natural history, including the variability and progression of the hereditary and acquired forms of the disease;
- Better understand the genotype – phenotype relationship in ATTRv;
- Compare the progression of disease and overall survival in patients with ATTR amyloidosis with and without liver transplant;
- Foster an international community of medical experts who will develop recommendations on the clinical management of ATTR amyloidoses;
- Provide information to better understand the management and treatment of patients with ATTR amyloidoses through publication of the survey data;
- Provide information on off-label use of tafamidis by identifying patients who do not meet the inclusion criteria for transthyretin amyloid cardiomyopathy (ATTR-CM)
- For tafamidis-treated patients, collect and summarize all AE/SAE data, including for the specific safety concerns outlined in Table 1 Summary of Safety Concerns to be Assessed in THAOS comprising important identified risks, important potential risks, and missing information that includes long-term safety in ATTR-CM patients with **CCI** [REDACTED] Class IV.
- For patients not treated with tafamidis, collect and summarize additional data on the events of interest listed in Table 1.

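### The SAP keeps an objective to compare survival with and without liver transplant, but plans only unadjusted Kaplan-Meier curves with groups defined by later transplant, so the comparison is confounded and carries immortal-time bias

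*SAP*

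**What the plan says.** Protocol 9.9 accepts that confounding biases treatment–outcome estimates and continues: "Analytical methods (like matching, multivariate regression) would be used to control for confounding". On incomplete data it says "Appropriate statistical methods would be employed to account for missing data and described in the SAP", and then "Sensitivity analysis to assess the impact of loss to follow-up will also be explored". Protocol 9.7.2 adds "Data will be summarized descriptively and modeled using appropriate statistical methodology".

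The SAP, written to support the final study report, keeps this objective in section 2.2: "Compare the progression of disease and overall survival in patients with ATTR amyloidosis with and without liver transplant". Protocol 8 carries the same objective. The SAP introduction also expects the safety data to give "additional information on the safety of tafamidis over the longer term as well as its effect on survival". SAP 4 then says: "There are no hypotheses associated with this survey. All analyses will be descriptive".

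The survival methods stand in SAP 6.2.1, 8.1 and 8.2.6. Time runs from enrollment in the untreated set and from first tafamidis dose in the treated set. Mortality is plotted by Kaplan-Meier, with a median and 95% CI when there are at least 5 events. The untreated set is split into transplant before enrollment, transplant after enrollment and no transplant. The treated set is split in the same way around the first dose. SAP 7 leaves missing values missing, apart from date imputation and questionnaire scoring rules.

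**The concern.** The planned outputs do not lead to the objective that the SAP retains. Three separate problems arise for overall survival.

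- **Confounding.** Protocol 7.1 lists liver transplantation among treatments for the polyneuropathy form, where onset with Val30Met is usually in the third to fourth decade. It describes the cardiac form as typically presenting after age 60, and combined heart and liver transplantation as limited by organ supply and co-morbidity. Transplanted and non-transplanted patients can therefore be expected to differ in age, genotype and phenotype. The untreated set also admits mutation carriers without disease. The transplant curves are not split by phenotype.
- **Immortal time.** A patient counts as transplanted after enrollment only by living long enough to receive the transplant, yet the clock starts at enrollment. Deaths before a possible transplant all fall in the no-transplant group. The treated set has the same structure, with the clock at first dose.
- **Loss to follow-up.** Kaplan-Meier assumes that patients who are lost have the same later risk as those who stay. The readable text plans no check of this.

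The curves go into the final report under an objective to compare, so they are likely to be read as the effect of transplant.

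**Working it through.** The documents give no event count, transplant rate, death rate, dropout rate, power or sample size (Protocol 9.1: "There is no pre-determined number of enrolled patients or participating sites in THAOS"). There is no planned figure to reproduce. The check sets the text side by side and then illustrates size under stated assumptions.

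**1. Text against text**

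| Stated | Readable survival plan in the SAP |
|---|---|
| Matching or regression for confounding (Protocol 9.9) | None in 6.2.1, 8.1 or 8.2.6 |
| Sensitivity analysis for loss to follow-up, to be explored (Protocol 9.9) | None |
| Missing-data methods in the SAP (Protocol 9.9) | Section 7: thin, but present |
| Data modeled (Protocol 9.7.2) | All analyses descriptive (section 4) |
| Survival compared by transplant status (SAP 2.2) | Separate curves; no between-group contrast |

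**2. Immortal time (simulation, assumed inputs)**

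Each scenario has 400,000 patients. Time to death and time to transplant are independent and exponential, with death rate λ = 0.05, 0.07 or 0.10 per year and transplant rate τ = 0.05, 0.10 or 0.20 per year. Follow-up is uniform over 1–12 years. The true transplant hazard ratio is 1. Groups and clock follow the SAP: transplant after enrollment against no transplant, timed from enrollment. The apparent hazard ratio is the ratio of deaths per person-year.

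- Over the nine combinations of λ and τ, the apparent ratio is 0.32–0.45.
- At λ = 0.07 and τ = 0.10, it is 0.41. Five-year Kaplan-Meier survival is 0.85 in the transplant group and 0.61 in the other. The true value in both is exp(−5 × 0.07) = 0.705.
- When each patient's time is counted as unexposed before transplant and exposed after it, the ratio returns to 0.99–1.01 in all nine.

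Hand check with complete follow-up: transplanted patients have mean time 1/(λ+τ) + 1/λ and the others 1/(λ+τ), so the ratio of rates is λ/(2λ+τ). At λ = 0.07 and τ = 0.10 this is 0.07/0.24 = 0.29. Limited follow-up softens it to the simulated 0.41.

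**3. Confounding (assumed inputs)**

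For one binary risk factor with hazard ratio h and prevalence p₁ in the transplant group and p₀ in the other, a true ratio of 1 appears as approximately [1 + p₁(h−1)] / [1 + p₀(h−1)].

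- h = 2: p₁ = 0.2, p₀ = 0.5 gives 1.2/1.5 = 0.80; p₁ = 0.3 gives 1.3/1.5 = 0.87.
- h = 3: p₁ = 0.2, p₀ = 0.5 gives 1.4/2.0 = 0.70; p₁ = 0.3 gives 1.6/2.0 = 0.80.

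If the factor is instead commoner in the transplant group, the ratios invert, from 1/0.87 = 1.15 to 1/0.70 = 1.43. The direction cannot be settled from the documents.

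**4. Loss to follow-up (assumed inputs)**

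If a fraction f is lost and crude mortality in the rest is m, true mortality lies between (1−f)m and (1−f)m + f. With f = 0.15 and m = 0.25 the limits are 0.85 × 0.25 = 0.21 and 0.21 + 0.15 = 0.36. The interval lies on both sides of 0.25. These are crude proportions, not Kaplan-Meier estimates.

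**5. Precision**

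With 5 events in each of two groups, the 95% CI for a hazard ratio spans a factor of exp(1.96 × √(1/5 + 1/5)) = 3.45 each way. For a hazard ratio of 0.5, 10 events give 19% power, and 80% power needs 66 events (Schoenfeld). Any adjusted model must depend on the event count.

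**The case against.** The strongest reply is that nothing binding has been broken. Protocol 9.9 is a limitations section in conditional wording, and Protocol 9.7.1 lets the SAP modify the plan, requiring an amendment only for major changes to primary endpoints or their analyses. This stands: a reader might infer a breached commitment, and the documents do not support that. However, the SAP did not modify the objective. It restated it. The readable amendment table explains why the repeated-measures models were dropped, but not the absence of confounding control or a loss-to-follow-up analysis.

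Other replies, and what remains of them:

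- **Curves by transplant status are a comparison of a kind.** Yes, and deaths by cause are tabulated for the same groups. It would be wrong to say the objective gets no answer. What is missing is an answer free of the biases above.
- **Tafamidis's effect on survival is not an objective.** Correct. It is introductory wording about a use of the data. The treated and untreated curves are also split by phenotype, so they are not wholly crude. The main point therefore rests on transplant.
- **Separate SAPs cover publications and other work (SAP 2).** An adjusted analysis may be planned elsewhere. This SAP still governs the final report and carries the objective.
- **Deaths and status updates are collected outside visits (SAP Table 2), and loss to follow-up is defined (Protocol 10.3).** This reduces the problem but does not test it.
- **Loss to follow-up must inflate survival.** This reading is tempting but unsupported. Bias arises only if loss is informative, and it can go either way.

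**Conclusion.** The concern holds for overall survival by liver transplant status. As planned, the contrast between transplant after enrollment and no transplant is confounded and has immortal time built in. The immortal-time part favors transplant. Under the assumed rates, a null effect would appear as a hazard ratio of about 0.32–0.45. That range rests on constant, independent death and transplant rates, and the registry's own rates would move it. Confounding could add to this or offset it.

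Loss to follow-up is an untested source of bias of unknown sign. The documents give no rate, but the SAP's Amendment 2 table (row for section 8.1) gives high drop-out as a reason for removing the repeated-measures models.

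No claim is made about progression, the other half of the objective: SAP 6.3 and 8.2.7 are redacted. Since the study is descriptive and the remedy is cheap, this is something that should be changed rather than a fatal defect.

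**What to change.** In SAP 8.2.6:

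(a) Add an exploratory Cox model for overall survival with liver transplant as a time-dependent exposure, adjusted for age, sex, genotype, phenotype and disease duration at entry. State how patients transplanted before enrollment enter the model. Fit it only where event counts allow, and report residual confounding and the number lost to incomplete covariates. If a tafamidis contrast is also wanted, make it time-dependent, use delayed entry for patients already on tafamidis at enrollment, and state how time after discontinuation is handled.

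(b) Add a sensitivity analysis for loss to follow-up. Censor lost patients at the date last known alive, since SAP 6.2.1 does not say which date ends their follow-up, and use, for example, inverse-probability-of-censoring weights. Show a run counting all lost patients as deaths only as an extreme bound; with high dropout it will say little.

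If (a) is not wanted, change *Compare* to *Describe* in SAP 2.2, remove the wording on effect on survival from SAP 2, and record the departure from Protocol 9.9.

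Cost: transplant dates, tafamidis dates, deaths and status updates are already collected, so the transplant model and the sensitivity run need programming only. Assessments are optional, so complete-case loss is likely. A tafamidis model costs more, because the present analysis sets exclude time after discontinuation. The wording route needs only a text change.

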#### **4.1 STATISTICAL HYPOTHESES**

Not applicable for this study.

#### **4.2 STATISTICAL DECISION RULES**

Not applicable for this study.

### **5 ANALYSIS SETS/POPULATIONS**

Analysis of clinical outcomes will be conducted on all enrolled patients with available data. Outcomes will be examined for the entire enrolled patient group, as well as through subgroups based on important variables that may affect outcomes (for example, but not limited to, TTR data, phenotype, CCI [REDACTED]). Outcomes will include results of the key clinical, functional and Patient Reported Outcome assessments used to define progression of disease.

#### **5.1 ALL ENROLLED**

This analysis set will include patients who have been enrolled in THAOS study and have signed the informed consent form.

The enrollment date will be considered as the date when informed consent form (ICF) was signed.

## 5.2 TAFAMIDIS UNTREATED

The tafamidis untreated set will include the following:

- All available data from patients who have been enrolled in THAOS, signed the informed consent and who have not received tafamidis during the THAOS study.
- All available data before receiving the first dose of tafamidis while in THAOS, for those patients who were not on tafamidis during or after initial enrollment in THAOS but then started receiving tafamidis post enrollment.

Note: Available data after a patient discontinues treatment with tafamidis will be excluded (See Figure 1)

## 5.3 TAFAMIDIS TREATED

The tafamidis treated set will include the following:

[figure not shown]
- All available data from the enrollment date until final treatment discontinuation of tafamidis or end of follow-up in THAOS (whichever is earlier) for patients who have been enrolled in THAOS, signed the informed consent and who were on tafamidis treatment on or prior to the date of enrollment in THAOS.
- All available data from first dose of tafamidis until final treatment discontinuation of tafamidis or end of follow-up in THAOS (whichever is earlier) for patients who were not on tafamidis at the time of enrollment in THAOS but subsequently initiated treatment with tafamidis.

Note: A patient can be considered part of both the tafamidis untreated and tafamidis treated sets if the patient initiated treatment with tafamidis after beginning participation in THAOS.

The below schematic will help to better understand the patient population to be analysed:

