## **11.2. Reporting Period**

For each patient, the safety event reporting period begins at the time of the patient's first dose of tafamidis or the time of the patient's informed consent if s/he is being treated with tafamidis at study start and lasts through the end of the observation period of the study, which must include at least 28 calendar days following the last administration of a drug under study; a report must be submitted to Pfizer Safety (or its designated representative) for any of the types of safety events listed in the table above occurring during this period.

If a patient was administered a drug under study on the last day of the observation period, then the reporting period should be extended for 28 calendar days following the end of observation.

Most often, the date of informed consent is the same as the date of enrollment. In some situations, there may be a lag between the dates of informed consent and enrollment. In these instances, if a patient provides informed consent but is never enrolled in the study (eg, patient changes his/her mind about participation), the reporting period ends on the date of the decision to not enroll the patient.

If the investigator becomes aware of a SAE occurring at any time after completion of the study and s/he considers the SAE to be related to tafamidis, the SAE also must be reported to Pfizer Safety.

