### **Exposure**

Duration of exposure (in years) among patients receiving tafamidis while enrolled in THAOS will be summarized (excluding time when the patient was part of clinical trial or Compassionate Use/Early Access Program) by starting dose using the tafamidis treated set by phenotype at enrollment and overall, CCI [REDACTED] and either predominantly cardiac or mixed phenotype at enrollment, tafamidis treated set for patients who had severe hepatic impairment at baseline, tafamidis treated set by liver transplantation status (liver transplant prior to first dose of tafamidis/liver transplant after the first dose of tafamidis/no liver transplant).

Additionally the duration of treatment with 20 mg and 61 mg/80 mg will be summarized separately for patients with off label use.

The duration of exposure (in years) will be calculated as:

Sum of all non-missing days when tafamidis was taken (excluding days of other clinical trial/compassionate use participation) / 365.25

Summary of exposure-adjusted Incidence rates (per patient-year) AEs and SAE for Treatment Emergent Adverse events (All causalities) and mortality for tafamidis treated set will be provided.

A separate listing will be provided for duration of exposure listing for patients who switched from 61/80 mg to 20 mg.

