### Adverse Events & Serious Adverse Events

All adverse events will be coded according to the latest Medical Dictionary for Regulatory Activities (MedDRA) version at the time of analysis.

Adverse events (all causality and treatment-related) will be summarized by severity and starting dose using the tafamidis treated set by phenotype at enrollment and overall, CCI [REDACTED] and either predominantly cardiac or mixed phenotype at enrollment, tafamidis treated set for patients who had severe hepatic impairment at baseline, tafamidis treated set by liver transplantation status (liver transplant prior to first dose of tafamidis/liver transplant after the first dose of tafamidis/no liver transplant).

Separate summaries will be provided for all AEs, treatment related AEs, all SAEs, treatment related SAEs, AEs leading to dose reduction, AEs leading to withdrawal of tafamidis (temporarily or permanently, or delayed) and AEs leading to tafamidis dose interruptions.

Listings will be provided for adverse events corresponding to all enrolled patients and for patients with off-label usage of tafamidis. A separate listing of SAEs will also be provided for tafamidis treated set.

The following AE summary tables will be provided corresponding to some of the important potential risks using the tafamidis treated set.

- For **hepatotoxicity** using the search criteria: MedDRA SMQ (Standardized MedDRA Query) [Broad and narrow] Drug related hepatic disorders – comprehensive search. The derivations and conventions related to the search criteria will follow the programming specifications done in the Periodic Safety Update Report (PSUR) 12 for tafamidis.
- For **reproductive and developmental toxicity and lactation**:
  - MedDRA SMQ (Broad and narrow): Congenital, familial and genetic disorders; Foetal disorders; Neonatal disorders, Neonatal exposures via breast milk.
  - MedDRA Preferred terms (PTs): Exposure during pregnancy, Exposure via father, Foetal exposure during delivery, Foetal exposure during pregnancy, Foetal exposure timing unspecified, Maternal exposure before pregnancy, Maternal exposure during delivery, Maternal exposure during pregnancy, Maternal exposure timing unspecified, Drug exposure before

- pregnancy, Exposure via breastmilk, Maternal drug affecting foetus, Maternal exposure during breastfeeding
- The derivations and conventions related to the search criteria will follow the programming specifications done in the PSUR 12 for tafamidis.

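### AE tables and rates for the tafamidis treated set pool patients followed from first dose with patients followed only from consent, so the pooled figure depends on the mix and has no fixed meaning as risk after initiation

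*SAP*

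**What the plan says.** SAP 5.3 defines the tafamidis treated set in two parts. The first is patients "who were on tafamidis treatment on or prior to the date of enrollment in THAOS", whose data count from enrollment. The second is patients "who were not on tafamidis at the time of enrollment in THAOS but subsequently initiated treatment with tafamidis", whose data count from first dose.

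Protocol 11.2 starts safety reporting at first dose, or at "the time of the patient's informed consent if s/he is being treated with tafamidis at study start". It sets no limit on how long such a patient may already have been treated.

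The outputs in SAP 8.2.6 then use the set as a whole:

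- Under Adverse Events & Serious Adverse Events: "Adverse events (all causality and treatment-related) will be summarized by severity and starting dose using the tafamidis treated set by phenotype at enrollment and overall". Further AE tables use hepatic impairment and transplant status. Separate summaries cover SAEs and AEs leading to dose reduction, withdrawal or interruption.
- Under Exposure: "Summary of exposure-adjusted Incidence rates (per patient-year) AEs and SAE for Treatment Emergent Adverse events (All causalities) and mortality for tafamidis treated set". The duration summary is of tafamidis time while enrolled, so years on drug before consent are not in it.

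No visible stratum in SAP 8.2.6, and no visible column in the SAP 8.2.8 summary table, separates patients already treated from patients who start in the registry. None uses time since first dose.

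**The concern.** This mixes new and prevalent users. A starter contributes the whole treatment course from day one. A patient already on drug contributes only a later part of it, and only because he or she was still taking tafamidis at consent. A patient who stopped before enrolling, perhaps because of an early event, contributes nothing as a continuing user.

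The pooled percentage is therefore neither the risk after starting tafamidis nor the long-term risk in patients who tolerate it. Exposure adjustment does not repair this: it corrects for how much time was observed, not for which part of the treatment course was observed.

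Comparisons between columns are affected too. Protocol 7.1 dates the first EU approval (polyneuropathy) to November 2011 and the cardiomyopathy approvals at 61 mg or 80 mg to 2019–2020, while the registry opened in 2007. The share of continuing users may differ between starting-dose columns for calendar reasons alone. Which column has more cannot be told from the documents, and the planned tables would not show it. These summaries serve a post-authorization safety commitment, so a reader will want to know what the frequencies refer to.

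**Working it through.** The plan states no AE rate, no sample size and no share of already-treated patients, so there is no figure to reproduce. The figures below are illustrations, and all hazards and shares are assumptions.

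**Inputs from the documents.** Follow-up starts at first dose or at enrollment (SAP 5.3). AE reporting starts at first dose or at consent (Protocol 11.2). Outputs are the percentage with an AE and events per patient-year on the pooled set (SAP 8.2.6).

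**Assumed inputs.** The AE hazard is 0.5/year in the first 6 months after first dose and 0.1/year after. Continuing users are past month 6 at enrollment. All patients have equal follow-up F. The share of continuing users is p = 20%, 50% or 80%. No selection of good tolerators is added.

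**Percentage with at least one AE**

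- Starters: 1 − exp(−[0.5 × 0.5 + 0.1 × (F − 0.5)])
- Continuing users: 1 − exp(−0.1 × F)
- Pooled: (1 − p) × starters + p × continuing
- Shortfall: (starters − pooled) / starters

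At F = 1, starters have 1 − exp(−0.30) = 25.9% and continuing users 1 − exp(−0.10) = 9.5%. At F = 5, the figures are 1 − exp(−0.70) = 50.3% and 1 − exp(−0.50) = 39.3%.

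| p | Pooled, F = 1 | Shortfall | Pooled, F = 5 | Shortfall |
|---|---|---|---|---|
| 20% | 22.6% | 13% | 48.1% | 4% |
| 50% | 17.7% | 32% | 44.8% | 11% |
| 80% | 12.8% | 51% | 41.5% | 17% |

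Two columns with identical true hazards, one with 20% and one with 80% continuing users, would thus show 22.6% against 12.8% at one year, or 48.1% against 41.5% at five.

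**Events per patient-year, same hazards.** At F = 1, starters have 0.30/1 = 0.30 and continuing users 0.10. Pooled rates are 0.26, 0.20 and 0.14, which are 13%, 33% and 53% below starters. At F = 5, starters have 0.70/5 = 0.14 and continuing users 0.10. Pooled rates are 0.132, 0.120 and 0.108, which are 6%, 14% and 23% below.

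**Does the direction depend on the hazard?** Let RR be the early hazard divided by the later hazard. In the first 6 months of observation, the pooled rate divided by the true early rate is [(1 − p) × RR + p] / RR:

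| RR | p = 25% | p = 50% | p = 75% |
|---|---|---|---|
| 0.5 | 1.25 | 1.50 | 1.75 |
| 1 | 1.00 | 1.00 | 1.00 |
| 2 | 0.88 | 0.75 | 0.63 |
| 3 | 0.83 | 0.67 | 0.50 |
| 5 | 0.80 | 0.60 | 0.40 |

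A constant hazard gives no distortion, and a rising hazard gives overstatement. The SAP plans no six-month table; these ratios show direction only.

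**A milder case over whole follow-up.** With RR = 3, a later rate of 0.30 per patient-year and p = 50%, pooled against starter rates are 0.45 against 0.60 at one year (ratio 0.75), 0.35 against 0.40 at three years (0.88) and 0.33 against 0.36 at five years (0.92).

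**The case against.** Several points on the other side stand.

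- A reader might infer that early events in continuing users are never collected. The documents do not support that. Protocol 9.3.5 allows any assessment listed in 9.3.1 to be entered retrospectively, that list includes AE/SAE reporting, and SAP Table 2 marks adverse events under optional retrospective visits. The entry is optional, however, and the treated set begins at enrollment, so such events stay outside the AE tables.
- A reader might also infer that early risk is certainly understated. That needs a hazard that falls with time on drug, or earlier loss of poor tolerators. Both are plausible, but the documents quantify neither.
- The one-year shortfalls of 13% to 51% should not be read as the size of the effect in this registry. SAP 8.2.6 plans no one-year risk. It summarizes events over all treated follow-up, and the visit windows in SAP Appendix 2 run to year 12. Dilution shrinks as follow-up lengthens.
- The survey is descriptive (SAP 4) and part of its stated use is longer-term safety (SAP 2), to which continuing users properly contribute. No passage presents the pooled frequency as risk after initiation. Protocol 9.9 acknowledges selection and ascertainment bias, though not this mechanism.
- The first part of the treated set includes patients who start on the enrollment date. They are not late entrants.
- Part of the AE stratification is blacked out, so the claim can only be that no split is visible. The adjoining wording suggests that the hidden stratum concerns cardiac patients, not prior treatment.

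None of this removes the core: the two groups are pooled with different entry points, and the planned tables cannot show whether that matters.

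**Conclusion.** The concern holds in conditional form. The pooled AE and SAE percentages and exposure-adjusted rates depend on the mix of starters and continuing users, both overall and across starting-dose or phenotype columns. They understate risk after initiation if AE risk falls with time on drug or if poor tolerators leave before enrolling.

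The size is not known. Under the single fivefold early excess assumed above, the understatement of the percentage ranges from about 4% (five years, 20% continuing users) to 51% (one year, 80%). This is a cheap improvement to a safety output, not a defect that invalidates it. The split would itself show whether the two groups differ.

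**What to change.** In SAP 8.2.6, for the overall treated set only, add one split of the AE, SAE and AE-led withdrawal summaries and of the exposure-adjusted rates into:

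- started tafamidis on or after enrollment;
- already on tafamidis before enrollment, with person-time counted from enrollment.

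Quote AE frequency after initiation only from the first group, and use the second for long-term exposure. State in the report that the second group enters late, that its events before consent are not systematically collected, and that patients who stopped before enrolling are not observed as continuing users.

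The data are in hand: SAP Table 2 logs tafamidis start and stop dates, and SAP 5.4 already uses tafamidis status at enrollment to define transplant subgroups. SAP 7 imputes a missing start day as the 15th, so the text should say how patients whose imputed start falls in the enrollment month are classed.

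The cost is SAP wording and one extra set of overall columns with smaller numbers. The phenotype, hepatic and transplant tables need not be crossed with the split. Doing so would push small cells to listings under the minimum of 10 patients in SAP 5.4 and 8.1.
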